### **8.3.3 Causality Collection**

The investigator should assess causal relationship between study intervention and each AE, and answer 'yes' or 'no' to the question 'Do you consider that there is a reasonable possibility that the event may have been caused by the study intervention?'

For SAEs, causal relationship should also be assessed for other medication and study procedures. Note that for SAEs that could be associated with any study procedure the causal relationship is implied as 'yes'.

A guide to the interpretation of the causality question is found in [Appendix B](#) to the CSP.

### **8.3.4 Adverse Events Based on Signs and Symptoms**

All AEs spontaneously reported by the patient or care provider or reported in response to the open question from the study site staff: "Have you had any health problems since the previous visit/you were last asked?" or revealed by observation will be collected and recorded in the eCRF. When collecting AEs, the recording of diagnoses is preferred (when possible) to recording a list of signs and symptoms. However, if a diagnosis is known and there are other signs or symptoms that are not generally part of the diagnosis, the diagnosis and each sign or symptom will be recorded separately.

### **8.3.5 Adverse Events Based on Examinations and Tests**

The results from the CSP-mandated laboratory tests, ECGs, and vital signs will be summarised in the CSR.

Deterioration as compared with baseline in CSP-mandated laboratory values, ECGs and vital signs should therefore only be reported as AEs if they fulfil any of the SAE criteria, are the reason for discontinuation of treatment with the study intervention, or are considered to be

clinically relevant as judged by the investigator (which may include but not limited to consideration as to whether treatment or non-planned visits were required or other action was taken with the study intervention, eg, dose adjustment or drug interruption).

If deterioration in a laboratory value/ECG/vital sign is associated with clinical signs and symptoms, the sign or symptom will be reported as an AE and the associated laboratory result/ECG/vital sign will be considered as additional information. Wherever possible the reporting investigator uses the clinical, rather than the laboratory term (eg, anaemia versus low haemoglobin value). In the absence of clinical signs or symptoms, clinically relevant deteriorations in non-mandated parameters should be reported as AE(s).

Deterioration of a laboratory value, which is unequivocally due to PD, should not be reported as an AE/SAE.

Any new or aggravated clinically relevant abnormal medical finding at a physical examination as compared with the baseline assessment will be reported as an AE unless unequivocally related to the disease under study.

### **8.3.6 Hy's Law**

Cases where a patient shows elevations in liver biochemistry may require further evaluation and occurrences of  $AST \text{ or } ALT \geq 3 \times ULN$  together with  $TBL \geq 2 \times ULN$  may need to be reported as SAEs. Please refer to [Appendix E](#) for further instruction on cases of increases in liver biochemistry and evaluation of HL.

### **8.3.7 Disease Progression**

Disease progression can be considered as a worsening of a patient's condition attributable to the disease for which the study intervention is being studied. It may be an increase in the severity of the disease under study and/or increases in the symptoms of the disease. The development of new, or progression of existing metastasis to the primary cancer under study should be considered as PD and not an AE. Events, which are unequivocally due to PD, should not be reported as an AE during the study.

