**Table 1 Schedule of Activities for Randomised Treatment**

Visit	Pre-screening	Screening	Intervention Period				Follow-up a			Details in CSP Section or Appendix			
			Cycle 1 (28-day cycle)				Cycles 2 to 6 (28-day cycle)	Cycle 7 onwards (28-day cycle)	Treatment discontinuation visit		28-Day follow-up visit b	Survival follow-up visit	
Week (Day 1 of)	NA	-4 to 0	1 to 4				5 to 24	25 onwards		Within 7 days of the final dose of study intervention			± 7 days
Study day		-28 to -1	1 to 28				29 to 168	169 onwards					
Day of cycle			1	8	15	22	1	1					
Visit window			± 1 day				± 3 days	± 3 days					
PK measurements													
Blood sample for PK analysis of savolitinib m, n			X n				Day 1 of Cycles 2, 3, and 6 n					8.5.1	
Blood sample for PK analysis of osimertinib m, n			X n				Day 1 of Cycles 2, 3, and 6 n					8.5.1	
Efficacy measurements													
Tumour imaging o (RECIST 1.1)		X p	Q6W (± 7 days) up to 24 weeks relative to randomisation, then Q8W (± 7 days) until objective disease progression									8.1	
Study intervention administration													
Dose with osimertinib or placebo			X (daily dosing)										6.1
Dose with savolitinib			X (daily dosing)										6.1

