### **2.3.1 Risk Assessment**

Investigators for a study using savolitinib monotherapy in patients with EGFRm+ NSCLC will be cognisant of the potential risk of rapid disease progression via EGFRm tumour driver reactivation. The NCCN Guidelines for NSCLC (NCCN 2020) include a warning about the risk of flare phenomenon occurring in patients who discontinue EGFR-TKI. Tumour flare after discontinuation of EGFR-TKI has been a recognised phenomenon for many years (Chaft et al 2011; Chen et al 2013) and indicates that the EGFRm sensitising mutation is not eliminated from the tumour following treatment with an EGFR-TKI in most patients. In some patients, this may cause a rapid clinical deterioration after discontinuing EGFR-TKI prior to entering the study (see Section 4.2.1). To minimise this risk, patients will be closely monitored over the first month of participation in the study to look for evidence of tumour flare. At investigator-assessed PD per RECIST 1.1, treatment allocation will be unblinded and those patients randomised to the savolitinib plus placebo arm will have the opportunity to cross-over to the savolitinib plus osimertinib regimen. Patients will be informed of the possibility of cross-over to savolitinib plus osimertinib during the informed consent process and at the time of progression on randomised treatment. Further risks and the respective mitigation steps are presented in Table 3.

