### **8.3.8 Disease Under Study**

Symptoms of disease under study are those that might be expected to occur as a direct result of locally advanced or metastatic NSCLC. Events which are unequivocally due to disease under study should not be reported as an AE during the study unless they meet SAE criteria or lead to discontinuation of the study intervention.

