### **8.3.10 Reporting of Serious Adverse Events**

All SAEs have to be reported, whether or not considered causally related to the study intervention, or to the study procedure(s). All SAEs will be recorded in the eCRF.

If any SAE occurs in the course of the study, then investigators or other site personnel inform the appropriate AstraZeneca representatives within one day, ie, immediately but **no later than 24 hours** of when he or she becomes aware of it.

The designated AstraZeneca representative works with the investigator to ensure that all the necessary information is provided to the AstraZeneca Patient Safety data entry site **within 1 calendar day** of initial receipt for fatal and life-threatening events **and within 5 calendar days** of initial receipt for all other SAEs.

For fatal or life-threatening AEs where important or relevant information is missing, active follow-up is undertaken immediately. Investigators or other site personnel inform AstraZeneca representatives of any follow-up information on a previously reported SAE within one calendar day, ie, immediately but **no later than 24 hours** of when he or she becomes aware of it.

Once the investigators or other site personnel indicate an AE is serious in the EDC system, an automated email alert is sent to the designated AstraZeneca representative.

If the EDC system is not available, then the investigator or other study site staff reports an SAE to the appropriate AstraZeneca representative by telephone.

The AstraZeneca representative will advise the investigator/study site staff how to proceed.

For further guidance on the definition of a SAE, see [Appendix B](#) of the CSP. Section 5.4 of the osimertinib and savolitinib IBs provides information related to the emerging safety profile of both study interventions.

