## **Appendix B Adverse Events: Definitions and Procedures for Recording, Evaluating, Follow-up, and Reporting**

### **B 1 Definition of Adverse Events**

An AE is the development of any untoward medical occurrence in a patient or clinical study patient administered a medicinal product and which does not necessarily have a causal relationship with this treatment. An AE can therefore be any unfavourable and unintended sign (eg, an abnormal laboratory finding), symptom (for example nausea, chest pain), or disease temporally associated with the use of a medicinal product, whether or not considered related to the medicinal product.

The term AE is used to include both serious and non-serious AEs and can include a deterioration of a pre-existing medical occurrence. An AE may occur at any time, including run-in or washout periods, even if no study intervention has been administered.

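### Sections 8.3.7 and 8.3.8 give opposite reporting rules for serious disease-related events, so serious non-fatal tumour flare may be recorded inconsistently in the AE and SAE tables

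*Supplement*

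**What the plan says.** Section 8.3.7 (Disease Progression) defines progression broadly, to include clinical worsening: "It may be an increase in the severity of the disease under study and/or increases in the symptoms of the disease". It then states the rule: "Events, which are unequivocally due to PD, should not be reported as an AE during the study". No exception is made for seriousness or for stopping treatment.

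Section 8.3.8 (Disease Under Study) covers events that are unequivocally due to the cancer. These are also not reported, but with an exception: "unless they meet SAE criteria or lead to discontinuation of the study intervention".

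Section 8.3.10 says: "All SAEs have to be reported, whether or not considered causally related to the study intervention".

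Appendix B 1 says: "The term AE is used to include both serious and non-serious AEs". Appendix B 2 defines an SAE as an AE that fulfils a seriousness criterion.

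On flare, Section 2.3.1 describes the risk of rapid progression when savolitinib is given without an EGFR-TKI and promises that "patients will be closely monitored over the first month of participation in the study to look for evidence of tumour flare". Section 4.2.1 repeats this, and the benefit/risk conclusion in Section 2.3.3 lists the same monitoring among its supports.

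**The concern.** A tumour flare is rapid worsening of the cancer, so it meets the 8.3.7 definition of progression. If it puts a patient in hospital without killing them, a site reading 8.3.7 does not report it, and a site reading 8.3.8 or 8.3.10 does.

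This trial depends on the answer more than most. One arm has no EGFR-TKI cover, and the protocol itself names deterioration after EGFR-TKI withdrawal as a hazard. Under Section 5.2 (criterion 15), osimertinib monotherapy may continue through screening. For patients who use that option, withdrawal begins with study treatment, and only in the savolitinib plus placebo arm. Osimertinib toxicities in the combination arm are counted as AEs under either reading. Serious harm from withholding osimertinib may or may not be counted. The AE and SAE comparison could then favour the placebo arm for a reason that lies in reporting, and the trial would be poorly placed to say whether its flare concern was borne out.

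**Working it through.** No sample size, power or event count bears on this point, and the plan gives no figure to reproduce. The check sets the rules side by side and follows one case through them.

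**Case.** A patient is hospitalised in Week 2 with rapidly worsening NSCLC symptoms. The investigator has no doubt that this is progression. The patient survives.

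| Section | Does it apply? | Result |
|---|---|---|
| 8.3.7 | Yes: progression includes worse symptoms or severity | Not an AE; no exception |
| 8.3.8 | Yes: the event is due to the disease under study | Reportable: hospitalisation meets SAE criteria |
| 8.3.10 | Yes, if the event is an SAE | Reportable |
| Appendix B 1 and B 2 | AE covers serious events; an SAE must first be an AE | A site that stops at 8.3.7 never reaches 8.3.10 |
| 8.3.5 (laboratory values) | By analogy | The PD exclusion there names SAEs explicitly |

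Sections 8.3.7 and 8.3.8 give opposite answers. Section 8.3.10 does not settle the matter, because its duty depends on the event counting as an AE. Section 8.3.5 shows that the protocol does, in one place, extend the exclusion to serious findings.

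**Where else the case would appear.**

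- *Deaths:* listed for all patients (9.4.3). This patient survived, so not here.
- *ECOG status, vital signs, physical examination:* scheduled on Days 1, 8, 15 and 22 of Cycle 1 (Table 1). Deterioration is visible if the visits are attended, but not as a serious event.
- *RECIST progression and PFS:* Table 1 schedules scans every 6 weeks (± 7 days) "up to 24 weeks relative to randomisation, then Q8W". The first falls between 42 − 7 = Day 35 and 42 + 7 = Day 49, after the 28 days of Cycle 1. Unscheduled scans are provided for (Appendix H 2.1) but not required.
- *PFS without a scan:* a patient with no evaluable visit is censored at Day 1 unless they die within two visits of baseline (9.4.2.2).

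The exposed category is therefore serious, non-fatal deterioration attributed unequivocally to progression, chiefly before the first scheduled scan.

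**Direction.** Let f be the share of such events that goes unreported, and let p1 and p0 be their true risks in the two arms. If f is equal in both arms, which blinding makes reasonable before the code is broken, the expected difference in the tables is (1 − f)(p1 − p0). At f = 0 (every site follows 8.3.8) nothing is lost. At f = 1 (every site follows 8.3.7) this component disappears. The distortion is toward no difference. The documents give none of f, p1 or p0.

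**The case against.** The strongest case on the other side is that this is a wording slip with several backstops.

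- **Only unequivocal events are barred.** Any event with a doubtful cause stays reportable. This stands: 8.3.7 does not exclude every progression-related event.
- **The safety assessment is wider than AEs.** Section 9.4.3 includes deaths, laboratory data, vital signs and ECOG status, and progression or death is compared by arm through PFS. A reader might infer that flare disappears from the safety comparison altogether. The documents do not support that; the gap is in the AE and SAE summaries.
- **First-month monitoring is real.** Weekly Cycle 1 visits are scheduled, and unscheduled scans can document early progression. This stands, but those visits do not tell a site whether to report the hospitalisation.
- **The imbalance is not established.** A reader might infer that nearly all such events would fall in one arm. Section 2.3.1 also speaks of EGFR-TKI discontinuation before study entry, and Section 5.1 (criterion 5) does not require osimertinib to be the latest therapy. Unevenness is plausible; its extent is unknown.
- **Loss of the IDMC.** A reader might count its removal as a lost safeguard. Section 9.6.1 gives it an efficacy role only, so the removal takes away no stated safety review.
- **AE analysis detail belongs to the SAP.** Section 9.4.3 says so and no SAP is shown, so the absence of a flare table is not a fault of the protocol. The conflicting site instructions are a protocol matter and remain.

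**Conclusion.** The point holds in a limited form. Sections 8.3.7 and 8.3.8 overlap and conflict, and 8.3.10 does not resolve them. Serious non-fatal deterioration from early progression or flare can therefore be missing from the AE and SAE summaries, or recorded differently across sites. This matters because Sections 2.3.1 and 2.3.3 rely on watching for that event.

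The number of affected events cannot be stated. It is tempting to multiply an assumed flare rate by the 28 patients per arm once planned, but the documents give no rate, and Section 9.2 says the planned number will not be reached.

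The conclusion assumes that some investigators apply 8.3.7 as written. The directional effect also assumes that flare is more frequent without osimertinib, which is the protocol's own rationale in Section 4.2.1. This is a correction that should be made; it does not affect the ORR analysis.

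**What to change.** 1. Reconcile 8.3.7 with 8.3.8 and 8.3.10 so that one reporting rule applies. One way is to give 8.3.7 the 8.3.8 exception for events that meet SAE criteria or end study intervention. Check the laboratory sentence in 8.3.5 against the same rule.
2. Identify such events as progression-related in the eCRF, so that AE and SAE totals can be shown with and without them.
3. Before unblinding, prespecify a table by randomised arm of patients with death, a serious disease-related event or RECIST PD on or before the first scheduled scan (Week 6 + 7 days, Day 49). Section 9.4 already requires the SAP to be final by then.

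**Cost.** A sentence, an identifier, one table and a few additional SAE reports, with no new visits or procedures. Some of the work is retrospective. Recruitment termination was decided on 22 February 2022 and Amendment 2 is dated 9 May 2022, which is 6 + 31 + 30 + 9 = 76 days later. Anyone randomised by the decision date had passed Day 49 before the amendment, so their early events need site queries. Only patients still in pre-screening or screening at termination and randomised afterwards (Section 4.1.4) could be covered prospectively.

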### **8.3.8 Disease Under Study**

Symptoms of disease under study are those that might be expected to occur as a direct result of locally advanced or metastatic NSCLC. Events which are unequivocally due to disease under study should not be reported as an AE during the study unless they meet SAE criteria or lead to discontinuation of the study intervention.

### **8.3.9 New Cancers**

The development of a new cancer should be regarded as an AE and will generally meet at least one of the serious criteria. New cancers are those that are not the primary reason for the

administration of the study intervention and have been identified after the patient's inclusion in this study. They do not include metastases of the original cancer.

### **8.3.10 Reporting of Serious Adverse Events**

All SAEs have to be reported, whether or not considered causally related to the study intervention, or to the study procedure(s). All SAEs will be recorded in the eCRF.

If any SAE occurs in the course of the study, then investigators or other site personnel inform the appropriate AstraZeneca representatives within one day, ie, immediately but **no later than 24 hours** of when he or she becomes aware of it.

The designated AstraZeneca representative works with the investigator to ensure that all the necessary information is provided to the AstraZeneca Patient Safety data entry site **within 1 calendar day** of initial receipt for fatal and life-threatening events **and within 5 calendar days** of initial receipt for all other SAEs.

For fatal or life-threatening AEs where important or relevant information is missing, active follow-up is undertaken immediately. Investigators or other site personnel inform AstraZeneca representatives of any follow-up information on a previously reported SAE within one calendar day, ie, immediately but **no later than 24 hours** of when he or she becomes aware of it.

Once the investigators or other site personnel indicate an AE is serious in the EDC system, an automated email alert is sent to the designated AstraZeneca representative.

If the EDC system is not available, then the investigator or other study site staff reports an SAE to the appropriate AstraZeneca representative by telephone.

The AstraZeneca representative will advise the investigator/study site staff how to proceed.

For further guidance on the definition of a SAE, see [Appendix B](#) of the CSP. Section 5.4 of the osimertinib and savolitinib IBs provides information related to the emerging safety profile of both study interventions.

### **8.3.11 Pregnancy**

All pregnancies and outcomes of pregnancy should be reported to AstraZeneca except for:

- If the pregnancy is discovered before the study patient has received any study intervention

If a pregnancy is reported, the investigator should inform the sponsor within 24 hours of learning of the pregnancy.

Abnormal pregnancy outcomes (eg, spontaneous abortion, foetal death, stillbirth, congenital anomalies, ectopic pregnancy) are considered SAEs.

#### **8.3.11.1 Maternal Exposure**

If a patient becomes pregnant during the course of the study, study intervention should be discontinued immediately.

Pregnancy itself is not regarded as an AE unless there is a suspicion that the study intervention under study may have interfered with the effectiveness of a contraceptive medication.

Congenital abnormalities/birth defects and spontaneous miscarriages should be reported and handled as SAEs. Elective abortions without complications should not be handled as AEs. The outcome of all pregnancies (spontaneous miscarriage, elective termination, ectopic pregnancy, normal birth or congenital abnormality) should be followed up and documented even if the patient was discontinued from the study.

If any pregnancy occurs in the course of the study or within 6 weeks of the last dose of study intervention, then the investigator or other site personnel informs the appropriate AstraZeneca representatives within one day ie, immediately but **no later than 24 hours** of when he or she becomes aware of it.

The designated AstraZeneca representative works with the investigator to ensure that all relevant information is provided to the AstraZeneca Patient Safety data entry site within one or 5 calendar days for SAEs (see Section 8.3.1) and within 30 days for all other pregnancies.

The same timelines apply when outcome information is available.

The PREGREP module in the eCRF is used to report the pregnancy and the PREGOUT is used to report the outcome of the pregnancy.

#### **8.3.11.2 Paternal Exposure**

Male patients should refrain from fathering a child or donating sperm during the study and 6 months following the last dose.

Pregnancy of the patient's partner is not considered to be an AE. However, the outcome of all pregnancies (spontaneous miscarriage, elective termination, ectopic pregnancy, normal birth or congenital abnormality), occurring from the date of the first dose until 6 months after the last dose and as indicated by previous studies (pre-clinical and clinical) should, if possible, be followed up and documented in the Pregnancy Report Form.

To capture information about a pregnancy from the partner of a male patient, the male patient's partner's consent must be obtained to collect information related to the pregnancy and outcome; the male patient should not be asked to provide this information. A consent form

specific to this situation must be used. The outcome of any conception occurring from the date of the first dose until 4 months after dosing ends should be followed up and documented.

### **8.3.12 Medication Error**

If a medication error occurs in the course of the study, then the investigator or other site personnel informs the appropriate AstraZeneca representatives within one day, ie, immediately but no later than 24 hours of when he or she becomes aware of it.

The designated AstraZeneca representative works with the investigator to ensure that all relevant information is completed within one (Initial Fatal/Life-Threatening or follow up Fatal/Life-Threatening) or 5 (other serious initial and follow up) calendar days if there is an SAE associated with the medication error (see Section 8.3.1) and within 30 days for all other medication errors.

The definition of a Medication Error can be found in [Appendix B](#).

